 Cognitive concern reported Objective evidence of impaired cognitive domain Persevered independence in functional abilities (ADCS-ADL >70%) Not demented (cognitive changes do not significantly impede social function or work activities) (Rule out vascular, other causes) Longitudinal decline (no lasting more than 3 years period at the enrolment time) Diagnostic and Statistical Manual of Mental Disorders, Fifth Edition, DSM – 5 	 CDR = 0.5 MMSE ≥ 25 Petersen/Winblad criteria, 1.5 SD in 1 or more domain Additional questionnaires: IADL/ADCS-ADL Montreal cognitive assessment (MoCa, ≥17) 	 CDR >0,5 MMSE ≤ 24 MoCa < 17 Petersen/Winblad criteria, 2 SD in 1 or more domain IADL below the limit of 70% 	

• Clinical Dementia Rating: The CDR® Dementia Staging Instrument uses a 5-point scale to characterise six domains of cognitive and functional performance applicable to dementia. The six domains are Memory, Orientation, Judgment & Problem Solving, Community Affairs, Home & Hobbies, and Personal Care. The rating is done by a semi-structured interview of the tested subject and a reliable informant or collateral source (e.g. a family member) referred to as the CDR® Assessment Protocol. Using the CDR® Scoring Table a subject's level of impairment/dementia is characterized: 0 = Normal, 0.5 = Very Mild Dementia, 1 = Mild Dementia, 2 = Moderate Dementia, 3 = Severe Dementia.

- Deliverable No. **D5.1** Version 1
- Mini Mental State Examination (MMSE): The MMSE is a brief, quantitative measure of cognitive status. It can be used to screen cognitive impairment, to estimate the severity of cognitive impairment at a given point in time, to follow the course of cognitive changes in an individual over time, and to document an individual response to treatment. Measurements of cognitive function include registration (repeating named prompts), attention and calculation, recall, language, ability to follow simple commands and orientation. Score of 24 or more (out of 30) is considered a normal cognition. Below this, scores can indicate severe (≤9 points), moderate (10−18 points) or mild (19−23 points) cognitive impairment.

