- Montreal Cognitive Assessment (MoCa): Due to ceiling effects in light MCI cases by the MMSE, the MoCa test will be used as well in assessing people affected by MCI. MoCa is a 30-question test that takes around 10 to 12 minutes to complete. MoCA evaluates cognitive abilities including Orientation, Short term memory/Delayed Recall, Executive Function/Visuospatial Ability, Language Abilities, Abstraction, Animal Naming, Attention and Clock-Drawing Test. Because it tests the executive function, it is considered more sensitive in this regard compared to MMSE.

In addition, the following inclusion and exclusion criteria must be fulfilled to enrol subjects in the study:

Inclusion criteria

- Male and female aged between 60 and 75 years.
- Al-Mind MCI assessment listed in table 2.
- Capable of giving signed Informed Consent, which includes compliance with the requirements and restrictions listed in the Informed Consent and in this protocol.

Exclusion criteria

- AI-Mind dementia criteria listed in table 2.
- History of cerebrovascular disease (i.e., major stroke episodes).
- Alcohol Dependence Scale AUDIT score positive.
- Severe medical disorders associated with cognitive impairment (organ insufficiencies, chronic infections, endocrine disorders) which produce chronic uncompensated failure.
- Severe head trauma with structural brain lesion and/or previous brain surgery.
- Severe mental disorders; Schizophrenia, known Major depression or bipolar disorder.
- Neuroimaging evidence of other potential causes of cognitive decline (e.g. subdural hematoma, brain malignancy, metabolic encephalopathy).
- History of non-brain malignancy < 5 years.
- Recent use of psychotropic drugs including AChEI and Memantine < 3 months.
- Participation in trials with experimental drugs.

The age specification is set between the age of 60 - 75 years at enrolment to avoid increasing confounding factors by age, causing cognitive function loss.

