There is a documented dementia uneven prevalence of 2:1 in MCI, affecting females more often than males (The Economist Intelligence Unit Limited, 2017). This epidemiological aspect will be addressed during the AI-Mind AI-tool developments and validation to ensure that relevant gender-associated biomarkers are not omitted. Due to this gender discrepancy, it can be hypothesised that there will be an increased prevalence of female-derived available and prospective data for inclusion, which could result in bias during tool development. Using state of art techniques to mitigate the bias of the AI algorithms development will ensure that the collected data is representative for both genders even though the data might be unbalanced due to the prevalence in female subjects.

Furthermore, unanimously at the General Assembly meeting on the 17th of September 2021, all sites decided to integrate supplemental SOA neuropsychological assessments to pre-screen potential

participants. These evaluations will be administered at each site during recruitment screening, covering different cognitive areas: memory, attention, executive functions, visuospatial skills and language. The scores obtained in these additional neuropsychological assessments will be included in Case Report Forms (CRF, table 3 and Annex I).

Table 3: Schedule of Activities

Procedure	Recruitment screening		Follow-up (weeks/months)			Notes
		то	T1	T2	Т3	
		0	8	16	24	
Informed consent signed	Х					
Inclusion and exclusion criteria	Х					
Sociodemographic and Anamnestic Data	Х					
Clinical history	Х					
Somatic and neurological physical examination	Х	Х	Х	Х	Х	
FFQ (Food frequency questionnaire)		Х				
Risk Factors	Х	Х				
Assessment of Somatic Comorbidity	Х	Х				
Current Therapy	Х	Х	Х	Х	Χ	
Memory Questionnaire	Х	Х			Χ	
AI-Mind MCI criteria, table 3	Х					
RAVLT (Rey Auditory Verbal Learning test)		X			Х	
ROCF (Rey-Osterrieth complex figure test)		Х			х	
Boston Naming Test		Х			Х	
Category Fluency		Х			Х	
TMT (A,B,B-A)		Х			Х	
Letter fluency		Х			Х	
128 lead EEG		Х	Х	Х	Х	
CANTAB – digitalised cognitive assessment		Х	Х	Х	Х	
MEG		Х			Х	only at UCM and HUH
Blood sample collection		Х				APOE, P-tau variance

Subgroup for MEG procedure

At UCM and HUH, a minimum of 70 patients per site will be measured with simultaneous M/EEG recordings. The localisation accuracy of MEG will be used for extracting the most relevant features for EEG data analysis.

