der)?	evere mental disorders (e.g. schizophrenia, known major depression or bipolar disor- Yes No euroimaging evidence of other potential causes of the cognitive decline (e.g. subdural

History of malignancy < 5 years? *	
O Yes	
O No	
Recent use of psychotropic drugs including AChEI and Memantine (< 3 months)? *	
O Yes	
O No	
MMSE ≤ 24 or MoCa < 17? *	
O Yes	
O No	
Petersen/Winblad criteria, 2 SD in 2/3 cognitive domain/according to MCI criteria *	
O Yes	
O No	
Positiv (I)ADL score (retained function) less than 70%? *	
O Yes	
O No	
Page break	
	Page 5

Mandatory fields are marked with a star *

ASSESSMENT SCALE RESULTS

Cognitive functioning

Cognitive fu	nctioning scale *
Specify which	n scale has been used to assess cognitive functioning .
O MMSE	
O MoCA	
Other (s	specify below)
Specify which	ch assessment scale was used to assess cognitive functioning *
	ment is only shown when the option "Other (specify below)" is selected in stion "Cognitive functioning scale"
Cognitive fu	nctioning scale score *
Ü	the score obtained with the assessment scale.
Activities	of Daily Living (ADL)
ADL scale *	
Specify which	h of the ADL scales has been used.
O IADL	
O ADL-MO	
Other (s	specify below)
Specify which	ch of ADL scales was used *
	ment is only shown when the option "Other (specify below)" is selected in stion "ADL scale"
ADL scale s	score *
Please enter	the obtained positive ADL score (i.e., the percentage of intact function).

Clinical Dementia Rating (CDR)

Use the calculator found here to compute the Global Score.

CDR scale G	Blobal Score *
Please enter t	he obtained CDR-Global Score.
Depressio	n
Depression s	cale *
Specify which	scale has been used to assess depression .
O MADRS	
O GDS	
Other (sp	pecify below)
Specify whicl	h assessment scale was used to assess depression *
This elem	nent is only shown when the option "Other (specify below)" is selected in ion "Depression scale"
Depression s	he score obtained with the assessment scale.
riodoo ontor a	To doore obtained with the doodselfield doubt.
Alcohol ak	ouse
Link to online	AUDIT screening.
Alcohol abus	e scale *
Specify which	scale has been used to assess alcohol abuse .
O AUDIT	
Other (sp	pecify below)
Specify whicl	h assessment scale was used to assess alcohol abuse *
	nent is only shown when the option "Other (specify below)" is selected in ion "Alcohol abuse scale"

Alcohol abuse scale score *	
Please enter the score obtained with the assessment scale.	
E Page break	
	Page

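### Participants who meet an exclusion criterion during follow-up are to leave the study, but the schedule does not systematically reassess those criteria after T0, and the progression limits carry no condition on cause

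*Protocol*

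**What the plan says.** **Entry (protocol, Section 3.3).** The MCI Criteria column of Table 2 carries the condition "Rule out vascular, other causes". The exclusion list names such causes, among them known major depression, a positive AUDIT, and "Severe medical disorders associated with cognitive impairment (organ insufficiencies, chronic infections, endocrine disorders" that amount to chronic uncompensated failure. The inclusion CRF in Annex I makes the site state which "scale has been used to assess depression" and enter the score, and does the same for alcohol.

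**Progression (Table 2).** The Dementia Progression Assessment column gives limits on CDR, MMSE, MoCA and standard deviations, and ends with "IADL below the limit of 70" per cent. It says nothing about cause.

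**Schedule (Table 3).**
- "Inclusion and exclusion criteria" and clinical history: screening only.
- "Assessment of Somatic Comorbidity" and risk factors: screening and T0 only.
- "Somatic and neurological physical examination" and "Current Therapy": screening and every visit from T0 to T3.
- Depression scale, AUDIT, imaging: no row of their own at any visit.

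**Drop-out (Section 5).** A participant who comes to meet an exclusion criterion during the two years is informed and leaves the study.

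**The concern.** The drop-out rule can work only if someone looks for the conditions that trigger it. A positive AUDIT needs an AUDIT, and a depression must be noticed before it is known. The schedule asks for neither after entry. Illness below the exclusion level is not covered by the rule at all, yet it could lower a test score past a limit such as 2 SD in one domain.

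Two participants with the same new illness and the same decline could thus be handled differently. One is dropped at a site that finds the cause; the other is counted as a progressor at a site that does not. The label is the reference standard for the primary sensitivity and specificity endpoints, both set above 0.9 (Table 1). A baseline EEG, genotype or p-tau value has no reason to predict a later unrelated illness, so such labels pull apparent sensitivity down.

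**Working it through.** **1. What the follow-up rows can detect.** Annex I shows only the inclusion form. Its examination page records height, weight, waist, blood pressure, cholesterol, neurological signs, sleep disorders and burnout or stress. Depression appears under clinical history and as a scale score, alcohol as a scale score, and organ disease on the comorbidity page. If follow-up visits use the same pages, the two rows repeated at T1 to T3 would show neurological signs and treated illness. They would not systematically show untreated depression, alcohol misuse or untreated organ disease.

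**2. The plan's own figure.** Section 5 states that 1000 participants suffice, with sensitivity = specificity = 0.9 and about 50% prevalence. This cannot be reproduced, because no alpha, interval width or test-set size is given. For orientation, with alpha = 0.05 assumed and all 500 progressors used, the 95% half-width is 1.96 × √(0.9 × 0.1/500) = 0.026.

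**3. Inputs for the illustration.**
- From the protocol: N = 1000; n = 500 true progressors (50%); classifier sensitivity 0.9.
- Assumed, with no source in the documents: 5–10% develop a confounding illness; one third of these cross a limit; crossing a limit is enough to be labelled a progressor; none is detected and dropped; n = 350 and n = 200 as lower alternatives.

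**4. False progressors.** Only the 1000 − n non-progressors can be wrongly labelled, so F = (1000 − n) × (0.05 to 0.10) × 1/3.

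**5. Cap on a perfect classifier's sensitivity** = n/(n + F).

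| n | F | Cap |
|---|---|---|
| 500 | 8.3 to 16.7 | 500/508.3 = 0.984 to 500/516.7 = 0.968 |
| 350 | 10.8 to 21.7 | 350/360.8 = 0.970 to 350/371.7 = 0.942 |
| 200 | 13.3 to 26.7 | 200/213.3 = 0.938 to 200/226.7 = 0.882 |

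**6. Apparent sensitivity of the planned 0.9 classifier at n = 500.** It calls 0.9 of true and 0.1 of false progressors positive:
- (450 + 0.83)/508.3 = 0.887
- (450 + 1.67)/516.7 = 0.874

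The loss of 0.013 to 0.026 is between half and all of the half-width in step 2.

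**The case against.** **Other causes are looked for after entry, and detected ones do not count as progression.** A reader might infer that the named causes are checked only at entry and that any resulting decline becomes dementia progression. The documents support neither. Examination and therapy are recorded at every visit, and recent psychotropic drug use is itself an exclusion, so a drug-treated depression could surface. Illness that reaches the exclusion level and is found leads to drop-out under Section 5. What remains is illness that is undetected or below that level.

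**Table 3 is not a full list of instruments.** It has no depression or AUDIT row at screening either, although the inclusion CRF collects both, and CDR, MMSE and MoCA have no rows of their own. Part of the annex is not available and follow-up forms are not shown. Participants also keep their ordinary hospital follow-up (Section 3.1). Collection outside Table 3 therefore cannot be excluded. Even so, at screening the eligibility row carries those items, and that row is not repeated. Local care also varies by site, while Section 1.1 aims for homogeneous procedures.

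**Nothing was dropped between matching columns.** The rule-out stands under MCI Criteria; the MCI Assessment column, which is the counterpart of the progression column, also lists limits without it. That is right. The accurate statement is that Table 2 has no criteria column for dementia, so no condition on cause is stated for progression.

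**The size rests on assumed rates.** This stands. A reader might apply the rates to all 1000 participants and get 17–33 false progressors, but a true progressor cannot become a false one. Nor do the figures show that a sensitivity above 0.9 is out of reach: at the protocol's 50% prevalence the cap stays well above 0.9, and it falls below only at the upper rate with 200 progressors.

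**Conclusion.** The point holds as a gap between the drop-out rule, the visit schedule and the progression limits. No scheduled follow-up item systematically reassesses the conditions on which Section 5 relies, and no condition on cause governs the progression label. The class of a participant with a new illness therefore depends partly on site habits.

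The effect is modest and conditional. At 50% prevalence it is 8–17 false progressors, a cap of 0.984–0.968, and about 0.89–0.87 observed for a true 0.9. This matters mainly because Section 5 plans at exactly 0.9, which leaves no margin against an endpoint above 0.9. The figures assume that no affected participant is detected and dropped and that one crossed limit suffices, although Table 2 states no any-or-all rule. Detection at some sites would shrink them. This is a worthwhile, inexpensive improvement and not a flaw that invalidates the design.

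**What to change.** 1. In Table 3, repeat at T3 the existing CRF comorbidity page and the depression and AUDIT scales, using for each participant the scale used at inclusion.
2. Flag participants whose decline has another recorded cause, and report the primary sensitivity and specificity with and without them.
3. Reconcile Table 2, the exclusion list, Table 3 and the drop-out paragraph of Section 5 on whether such participants are dropped, counted as progressors or flagged. The flag in item 2 depends on this, because the present drop-out rule would remove some of them before T3. The same reconciliation should cover the fact that the exclusion list contains the dementia criteria themselves, so that read literally the rule also removes true progressors.

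Cost: a schedule and CRF amendment and a slightly longer T3 visit, with no new instrument. Causes not recorded during follow-up may be impossible to recover at analysis.

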3.4 Timetable of the Clinical Study

The schedule for study conduct, including timelines for key study milestones within the project timeframe, is presented in *figure 1*.

Figure 1: Diagram of the study conduction with key milestones; **FPFV** = first patient first visit; **FPLV** = first patient last visit; **LPFV** = First patient last visit; **LPEV** = last patient last visit

3.5 Informed Consent

Following the EC requirement, the coordinator (OUS) created a Study Information Sheet in English, which included necessary information about the Al-Mind project, including Al-Mind's appointed overall responsible study Data Protection Officer (DPO). This document was used to create each country specific "Informed Consent".

All clinical sites followed their local and national procedures and incorporated the study-specific details provided by the overall "Information Sheet", along with the local requirements from the Ethics Committees. In addition to the national user organisations` input, the Italian sites incorporated in the Informed Consent feedback from Alzheimer Europe and the European Working Group of People with Dementia. An Informed Consent tracking log has been created for each clinical site, to record any potential further amendments to the Informed Consent documents. Informed Consents will be signed and stored in paper form in all sites, except for Norway (OUS). Here the consent is given digitally, complying with the local laws and regulations. All signed documents will be stored according to current local clinical site requirements, following the Personal Data Act/GDPR.

For more details regarding the Informed Consent procedures and the approved documents at each site, refer to Deliverable 9.1.

3.6 Case Report Forms

The Case Report Forms (CRF) are designed to collect all textual information related to initial screening, and, following inclusion, other textual data, e.g. socio-demographic information. All national CRFs are digitally implemented in "Nettskjema" (digitalised web-form) provided by the University of Oslo (UiO). The Nettskjema service transfers the information in a highly secure way directly to the site-specific directories for storage on the TSD server.

Authorised national staff from the clinical sites will enter the data in the electronic form. The delegation of tasks to specific clinical personnel will be done by the Principal Investigators at each clinical site and documented in the "Delegation Log" file (see Deliverable 9.1).

Identification numbers

Two different identification numbers will be used for screening and final inclusion of subjects in Al-Mind:

- Local inclusion ID: a local numbering system, selected by each site, to track the potential
 participant before confirming eligibility to qualify for study participation. The local ID numbers
 will not be used for data integration on the project's centralised platform. Each site is
 responsible for maintaining a list connecting the Local Inclusion ID with the AI-Mind participant
 ID
- AI-Mind participant ID: when a subject fulfils the inclusion criteria, a unique number will be given, according to the harmonised pseudonymisation process (described in Deliverable 2.1).
 All nationally collected data will be marked with a unique AI-Mind participant ID, which along with the Site ID and Visit ID, and create a unique Session ID, with which the data entered in the platform will be associated with each participant.

An overview of the electronic CRF forms, the inclusion process, and the use of identification numbers is presented in *figure 2*. The electronic CRF forms may be found in Annex I.

[figure not shown]

Figure 2: Electronic forms for screening and data collection.

3.7 Instrumental clinical procedures

In this subchapter, the used instrumental clinical procedures are briefly presented. For specific technical details of these procedures, refer to Deliverable 2.1.

Electroencephalography

Empowered EEG recordings will be done at all clinical sites. Resting state (RS) data (three times five-minute intervals; eyes-open, eyes-closed, eyes-open) will be recorded by a 128-channel device, identically procured at all the centres². EEG data will be pre-processed using a semi-automatic pipeline defined in WP2, including SOA procedures for detection and management of signal noise and other artefacts. Moreover, a set of programmed and voluntary reproduced artefacts will be collected at the beginning of each session (harmonised procedures for all clinical centres in order to better identification).

Magnetoencephalography

MEG recordings will be done at two clinical sites: HUS and UCM. MEG recordings will be performed using standard procedures (Gross et al., 2013) with MEGIN systems (306-channel). Data will be collected at a sampling frequency of 2000 Hz and online band-pass filtered between 0.1 and 660 Hz. The MEG protocol will be identical with the EEG protocol. MEGs will be recorded at two-time points (visits 1 and 4). MEG and EEG measurements are conducted simultaneously.

Genetic and protein analysis

Blood sample for DNA isolation and plasma protein assessment will be collected from participants in the morning of the first visit, with participants non-fasting. Collection, storage, and shipment procedures have been standardised by the "Standard Operating Procedure" authored by the responsible blood analysing partner OUS (see Deliverables 2.1 and 9.4).

Genetic analysis of the $\epsilon 4$ allele of APOE is the strongest genetic risk factor for AD compared to those carrying the more common $\epsilon 3$ allele (Lambert JC, et al., 2009; Corder et al., 1994). The presence of this allele is associated with increased risk for both early-onset and late-onset AD, while allele ϵ 2 is protective. In the future AI model, the genetic data will be beforehand classified either as increased-risk or not. The determination of phosphorylated form of tau (P- tau 181) may increase the specificity and sensitivity in the detection of AD. Other genetic biomarkers, that may eventually stem from research during the course for the AI-mind project, will be potentially added for further evaluation (besides ApoE and P-Tau 181, -217).

Cambridge Neuropsychological Test Automated Battery (CANTAB)

The digital cognitive assessment (CANTAB) is an innovative cloud-based product that is validated for use on an iPad. The AI-Mind CANTAB data set contains 9 well-validated neuropsychological tests, all administered in the 4 national languages (Norwegian, Spanish, Italian and Finnish). The selected tests are non-language specific and European culture-independent, highly sensitive/specific and suitable for use in a wide-range of cognitively affected MCI population. CANTAB will be carried out at each visit (T0, after 8, 16 and 24 months). Each session lasts for 38 – 45 mins.

Classical NPTs scores from the standard subject follow-up will be collected for the selected CANTAB test validation. The classical NTP test battery includes tests of executive function and behaviour (Trail Making Test, Stroop colour-word test, Frontal Assessment Battery); memory test score (Rey's word list learning immediate and delayed recall; Rey Osterrieth figure immediate and delayed recall),

-

² In principle, the Al-Mind Connector algorithm will later also be applicable for lower number of recording channel systems (32- or 64-channels).

visuospatial function (Copy of Rey's figure) and language tests (Phonological and semantic verbal fluency).

Medical Devices

All medical devices used in this study have been routinely employed in clinical use for several decades, except MEG, which has been used for around twenty years. All device deficiencies (including malfunction, use error and inadequate labelling) shall be documented and reported by the local investigators throughout the clinical investigation and appropriately managed by the management support team of the Al-Mind project.

